	
pharmacists, and the HIV treating physician Source - http://www.hcvguidelines.org/full-report/unique-patient-populations-patients-hivhcv-coninfection
 
(2). In patients who are taking warfarin, Protime and INR values will be obtained weekly during and following the study to determine if there are any alterations in the Protime and INR due to a Zepatier-Warfarin interaction. Any alterations will result in warfarin dosage adjustments to achieve therapeutic anticoagulation as measured by Protime and INR
 
8. . Testing/Evaluations During Active Treatment
 
a. Liver function tests and RNA viral load at week 4 (only in patients with Child’s A cirrhosis), 8, and 12 of treatment. For patients on 16 week therapy, LFT also at week 16.
 
b. In patients who are treated with combination of Zepatier and Ribavirin, hemoglobin monitoring every week during course of treatment
 
c. Clinical Pharmacology evaluation for compliance and adverse events at week 4, 8, and 12 (and week 16 for patients receiving a 16 week treatment course).
 
9.. Testing/Evaluation Post Treatment
 
a. RNA viral load at 12 weeks post treatment
 
b. Clinical Pharmacology evaluation 12 weeks post treatment for adverse events and determination if a SVR was achieved at 12 weeks post treatment
 
c. Patients who have a SVR at 12 weeks will be identified in the hemodialysis treatment records as hepatitis C ab positive but hepatitis C viral RNA PCR negative

2.6 Study Duration
	
It is estimated all subjects will be recruited and complete treatment over a 9 to 12 month period of time

2.7 Statistical Analysis and Sample Size Justification
	
The co-principle investigators [name] and [name] will be responsible for analyzing all data Since this study does not have a control or comparator group, issues of blinding are non-applicable
 
Statistical Methods
 
The planned primary analysis will be the proportion of patients who following treatment have achieved a SVR at 12 weeks following completion of treatment.

[figure not shown]

Secondary analyses will determine (a) proportion of patients for whom third party approval for Zepatier treatment was successfully obtained (b) logistic barriers to getting third party approval (c) adverse events with treatment

The design of this protocol does not require any specific statistical methods to test the hypothesis

Power/Sample Size:

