
2.13 Protocol Submission for Investigator-Initiated Studies
	
U.S. protocols should be submitted by US investigators directly or through the Global Research Specialist at www.merckiisp.com
 
Non U.S. protocols should be submitted to the MSD office by the investigators.

Study Procedures

Hepatitis C antibody testing is performed routinely as per unit protocol for the clinical care of dialysis patients. These standard of care labs will be reviewed and Hepatitis C antibody positive patients identified. Patients will have a Hepatitis C viral load and genotype performed. Patients who are viral load positive and genotype 1 or 4 will be eligible to participate and approached about the study.

	Visit 0	Visit 1	Visit 2	Visit 3-5	Visit 6
Study week	prescreening	enrollment	1	4,8,12	24
Review HCV Ab results	X				
HCV viral load and genotype	X				
Sign informed consent		X			
NS5a testing		X (genotype1 only)			
LFTs, PT, PTT, INR, Hepatitis B, HIV		X			
Fibroscan or review of liver biopsy		X			
Referral to Hepatology		X (only for patients with cirrhosis)			
Referral to ID		X (only for patients with HIV)			
Review by Transplant Nephrology		X (evaluate potential for transplant, review listing status)			
Apply for Insurance approval		X			
Start study drug			X		
LFTs			X	X	
HCV VL			X	X	X
Hemoglobin			X (only if on Ribavirin)	X (only if on Ribavirin)	
Adverse event assessment				X	
Compliance assessment				X	

Patients who consent to participate will have a NS5A polymorphism checked in order to determine if Ribavirin administration is required. Study drug(s) will be administered as follows:

Genotype	NS5A	Prior treatment	Drug(s)	Duration
1a	no	no	Zepatier	12 weeks
	yes	no	Zepatier + Ribavirin	16 weeks
	no	yes	Zepatier + Ribavirin	12 weeks
1b	n/a	no	Zepatier	12 weeks
	n/a	yes	Zepatier + Ribavirin	12 weeks
4	n/a	no	Zepatier	12 weeks
	n/a	yes	Zepatier + Ribavirin	16 weeks

Subjects will be instructed to take Zepatier + ribavirin at bedtime. Phosphate binders should be taken at least 3 hours before or 3 hours after taking the Zepatier + ribavirin. If a subject misses a dose of Zepatier + ribavirin and it is less than 8 hours before the next dose, the missed dose should be skipped and the normal dosing schedule resumed. Subjects should not double the next dose to compensate for the missed dose.

Subjects may withdraw consent at any time for any reason or be dropped from the trial at the discretion of the investigator should any untoward effect occur.

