 - j. For patients with a history of intravenous or alcohol abuse, documentation will be needed to demonstrate that a discussion occurred with the patient discussing the risks of substance abuse and that the provider has offered to get substance abuse help for the patient
 - k. Additional baseline/screening testing/information will be obtained if requested by a third-party payer as a requirement for drug approval
 - l. One office visit for all candidate patients with a hepatologist or infectious disease physician with expertise in hepatitis C management before treatment is initiated to review all laboratory and clinical

history data. At this visit, there will be a determination of the fibrosis stage, including the presence or absence of cirrhosis and to guide optimal choice of therapy as well as determine if there is a need for long term cirrhosis management and liver cancer surveillance. Further office visits with this physician will be determined on presence/absence of cirrhosis and otherwise on an as needed basis as determined by the dialysis nephrologist.

m. Treatment of HIV/HCV co-infected patients will need to be done in collaboration with the patients primary HIV provider prior to starting and during HCV therapy to determine if any adjustments to the HIV regimen will need to be undertaken:

(1). Zepatier can be used with antiretroviral drugs which do not have significant interactions with Zepatier : abacavir, emtricitabine, enfuvirtide, lamivudine, raltegravir, dolutegravir, rilpivirine, and tenofovir. Other antiretroviral drugs allowed will be determined based on package insert, consultation with specialty pharmacists, and the HIV treating physician

Source - <http://www.hcvguidelines.org/full-report/unique-patient-populations-patients-hivhcv-coninfection>

Testing/Evaluations During Active Treatment

a. Liver function tests and RNA viral load at week 4 (only in patients with Childs A cirrhosis), 8, and 12 of treatment. For patients on 16 week therapy, LFT also at week 16.

b. In patients who are treated with combination of Zepatier and Ribavirin, hemoglobin monitoring every week during course of treatment

c. Clinical Pharmacology evaluation for compliance and adverse events at week 4, 8, and 12 (and week 16 for patients receiving a 16 week treatment course).

Testing/Evaluation Post Treatment

a. RNA viral load at 12 weeks post treatment

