- Describe the follow-up of subjects and identify any procedures that are performed exclusively for research purposes or performed more frequently than would be clinically indicated (eg: additional x-rays)
- You may upload additional documentation using the **Upload** button below

Since this is a real-world study, all procedures and interactions performed are standard of care in the treatment of dialysis patients with Hepatitis C infection. We will review standard of care Hepatitis C antibody results and follow up any positive results with a Hepatitis C viral load and genotype. Patients who are viral load positive with genotype 1 or 4 infection will be approached about study participation during a standard of care dialysis visit. Patients who consent to the study will have LFTs, Hg, PT, PTT, INR, HIV and Hepatitis B testing performed, these are all the standard laboratory testing required to safely initiate Hepatitis C treatment. We will refer all patients to Hepatology for an evaluation of their fibrosis stage (either by biopsy or fibroscan, at the discretion of the hepatologist); patients who have stage 4 fibrosis (ie cirrhosis) will only be treated in consultation with hepatology. Patients who are HIV co-infected will be referred to infectious disease and their treatment will only be undertaken in consultation with ID. Pharmacy will go through the necessary steps to obtain insurance approval for the medications but all medications will be provided by the study sponsor. Patients will be started on the study drug and have standard of care laboratory tests performed to monitor liver function while on the medication (LFTs and Hepatitis C viral load; hemoglobin will be followed in patients on ribavirin). Once the study drug is completed, patients will have a final Hepatitis C viral load checked 12 weeks after the completion of therapy to document a cure.

The following documents are currently attached to this item:

Procedures (studyprocedures.docx) Date uploaded: 02/27/2018 10:27:30 AM

Deception

No

Are you conducting research outside of the United States? *

No

Analysis Plan

- **Note:** If the statistical methods used are described in the detailed protocol, this section may reference the detailed protocol.

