Zepatier is FDA approved to treat Hepatitis C in dialysis patients. Therefore the risks of participating in this study are the same as the subject would encounter being treated with Zepatier in a non-study setting. These risks include side effects of nausea, headache and fatigue. There is the possibility of Hepatitis B reactivation with any treatment for Hepatitis C in patients who are co-infected, therefore we will monitor Hepatitis B levels in patients who are co-infected and if detectable, institute treatment for Hepatitis B in consultation with hepatology. When treating Hepatitis C there is always the possibility of liver inflammation and increases in LFTs, we will monitor these every 4 weeks. Patients with advanced liver disease (ie cirrhosis) are at risk for hepatic decompensation when being treated for Hepatitis C - we will not treat patients with cirrhosis ourselves, but instead refer them to hepatology and let hepatology manage their treatment. Patients who are on warfarin may have a Zepatier-Warfarin drug interaction - in these patients Protime and INR will be monitored weekly during the study

Potential Study Benefits

This study will provide clear benefit to participants as they will be treated for their Hepatitis C infection at no cost to them. They will also add to the general medical knowledge by demonstrating the feasibility of general nephrologists treating Hepatitis C infection and identifying the difficulties in achieving this.

Alternatives to Participation (optional)

If the participant chooses not to participate in this study, their doctor will continue to follow the standard of care practices at the University of Pennsylvania Health-System. The participant can also discuss this with their doctor at any time

Data and Safety Monitoring

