The risks of participating in the study are similar to the risks the subject would encounter being treated for Hepatitis C outside of the study setting and the benefit to be obtained is significant as study subjects will have access to Hepatitis C treatment free of charge. Given that all laboratory testing to be performed will be done as per standard of care and obtained from the patients while they are already on dialysis, this is a minimal risk study.

[Back to submission activity](#)

[Previous](#)

[Next](#)

Send questions or comments about this site to: [contact] or [contact] - Please do not include confidential information in your Email.

Copyright © 2007, [University of Pennsylvania](#). All rights reserved.
[Statement on privacy](#).

Basic Info	Personnel	Bio	Sponsors	Sites	Protocol	Populations	Procedures	Consent	Risk/Benefit	Change Log
------------	-----------	-----	----------	-------	----------	-------------	------------	---------	--------------	------------

Protocol Form - Status

Documents already attached on previous pages

[Procedures \(studyprocedures.docx\)](#) Date uploaded: 02/27/2018 10:27:30 AM

Additional forms or documents

Cover Letter (with additional information that may help in the review)

The following documents are currently attached to this item:

[Cover Letter \(irbhepcoverletterresponse.docx\)](#) Date uploaded: 07/15/2018 06:36:12 AM

[Cover Letter \(merckcoverletter.docx\)](#) Date uploaded: 02/27/2018 10:53:56 AM

Full sponsor's protocol

The following documents are currently attached to this item:

[Full sponsor's protocol \(irb-studyprotocoltrackedchangeszeptatierinhepatitiscinhemodialysis7-14-18.doc\)](#) Date uploaded: 07/15/2018 06:37:05 AM

[Full sponsor's protocol \(irb-studyprotocolcleanversion-zeptatierinhepatitiscinhemodialysis7-14-18.doc\)](#) Date uploaded: 07/15/2018 06:37:39 AM

[Full sponsor's protocol \(merckmispprotocoltemplate11-14-17version2.doc\)](#) Date uploaded: 02/27/2018 10:47:35 AM

Grant Application (minus the appendices & budget information, for federally-funded studies, e.g. NIH, CDC, DOD)

There are no documents attached for this item.

Performance site approvals for sites other than Penn (this does not apply to other participating sites which have their own IRB.)

There are no documents attached for this item.

Informed consent form (and parental permission/assent form for research involving children)

The following documents are currently attached to this item:

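### The protocol gives conflicting on-treatment LFT schedules: the procedure text limits week 4 to Child's A cirrhosis, while the visit table and the Risk section do not

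*Protocol*

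**What the plan says.** Four parts of the protocol describe liver monitoring during treatment.

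- **Procedure text.** Study Procedures, Testing/Evaluations During Active Treatment, item a, asks for "Liver function tests and RNA viral load at week 4 (only in patients with Childs A cirrhosis), 8, and 12 of treatment". Section 2.5 item 8a has the same restriction and runs on: "A cirrhosis), 8, and 12 of treatment. For patients on 16 week therapy, LFT also at week 16".
- **Visit table** (Study Procedures). The LFT row is marked at Visit 2 (week 1, the visit labelled "Start study drug") and at Visits 3-5 (weeks 4, 8 and 12), with no subgroup limit. Other rows do carry limits: NS5A testing to genotype 1, hepatology referral to cirrhosis, hemoglobin to ribavirin. The table has no week-16 column.
- **Potential Study Risks.** As the safeguard against hepatic inflammation, it says "there is always the possibility of liver inflammation and increases in LFTs, we will monitor these every 4 weeks".
- **Procedures summary** (Protocol Form - Study Procedures). Patients will "have standard of care laboratory tests performed to monitor liver function while on the medication (LFTs and Hepatitis C viral load", again with no restriction by cirrhosis status.

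**The concern.** Staff who follow the procedure text would schedule no LFT between drug start and week 8 in a patient without cirrhosis. Staff who follow the table or the Risk section would draw one at week 4. An asymptomatic ALT rise in the first half of treatment could therefore be found or not depending on which page is used.

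Three things rest on this schedule.

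- **The discontinuation rule.** Treatment stops for an ALT elevation around ten times the upper limit that persists. Seeing persistence on scheduled tests takes two of them.
- **The secondary analysis of adverse events.** Section 2.9 counts unfavorable laboratory results as adverse events, so the number of ALT events found depends on how often LFTs are drawn.
- **The study's own product.** The choice of on-treatment monitoring tests is listed among the primary outcome variables, and the results are meant to become guidance for nephrologists.

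The ethics submission described monitoring every 4 weeks as a protection. The detailed procedures do not deliver it to patients without cirrhosis.

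**Working it through.** The documents state no figure to reproduce, so the check is to list the schedules and count.

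**Inputs.** Procedure text: Study Procedures, Testing/Evaluations During Active Treatment, item a, and section 2.5 item 8a. Table: Study Procedures, LFT row. Risk section: Potential Study Risks, with every 4 weeks read as weeks 4, 8 and 12, plus 16 on the longer course. Course lengths of 12 and 16 weeks come from the dosing schedule. Sample sizes are about 30 (section 2.7) and 25 (SAP).

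**LFT weeks after the start visit, with the count in brackets**

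| Patient, course | Procedure text | Visit table | Risk section |
|---|---|---|---|
| No cirrhosis, 12 weeks | 8, 12 (2) | 4, 8, 12 (3) | 4, 8, 12 (3) |
| No cirrhosis, 16 weeks | 8, 12, 16 (3) | 4, 8, 12 (3) | 4, 8, 12, 16 (4) |
| Child's A, 12 weeks | 4, 8, 12 (3) | 4, 8, 12 (3) | 4, 8, 12 (3) |
| Child's A, 16 weeks | 4, 8, 12, 16 (4) | 4, 8, 12 (3) | 4, 8, 12, 16 (4) |

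Counting the table's week-1 mark raises every visit-table entry to 4. Only the Child's A 12-week row agrees across all three sources.

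**Dosing weeks left at the first LFT after drug start, no cirrhosis** (course length minus week of first LFT)

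- Text: 12 - 8 = 4 and 16 - 8 = 8.
- Table (after the start visit) and Risk section: 12 - 4 = 8 and 16 - 4 = 12.

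**Earliest point at which two scheduled tests could show persistence, no cirrhosis, 12-week course**

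- Text: weeks 8 and 12, leaving 12 - 12 = 0 dosing weeks.
- Table (after the start visit) and Risk section: weeks 4 and 8, leaving 12 - 8 = 4.

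**Viral load.** The restricting parenthesis follows the words for week 4, so it covers both tests named in the sentence. The table marks viral load at week 4 for all, so that test conflicts too.

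**The case against.** The strongest reply is that the conflict is partly a matter of document age. The procedures attachment is dated ("Procedures (studyprocedures.docx) Date uploaded: 02/27/2018"), while a clean protocol was uploaded on 07/15/2018. The attachment does look out of date: it still requires an office visit where section 2.5 has a record review, and it lacks the warfarin monitoring. The table is also coarse. It pools Visits 3-5 under one mark and shows hemoglobin only at visits, although the text asks for it weekly. On this view both detailed texts agree on the Child's A limit and should govern.

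This weakens the table as evidence but does not settle the matter. Section 2.5 still contradicts Potential Study Risks, which includes the warfarin monitoring and so appears current. The attachment also remains listed in the submission, under "Documents already attached on previous pages". Section 2.4, Study Flowchart, shows nothing under its heading in the text reviewed, and a figure may be missing there. A figure could not make two explicit, opposing sentences agree.

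Several points on the other side stand:

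- Less monitoring could be a legitimate choice, in which case the table and the Risk section are what is wrong.
- Other routes to detection exist: the week-4 adverse event review, the clinical pharmacologist's scheduling of labs with the investigator, investigator discretion to stop treatment, and unscheduled repeats.
- The table's only post-treatment column is week 24, which on a 16-week course is 24 - 16 = 8 weeks after treatment. That is a separate fault in the table.

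Who manages cirrhosis ("patients who have stage 4 fibrosis (ie cirrhosis) will only be treated in consultation with hepatology") does not matter here, because the gap concerns patients without it.

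**Conclusion.** The concern holds and should be fixed. For a patient without cirrhosis on 12 weeks, the procedure text lists 2 LFTs after the start visit against 3 in the table and the Risk section, and the first comes at week 8 instead of week 4. On 16 weeks the counts are 3, 3 and 4, with week 4 missing from the text and week 16 missing from the table.

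This rests on the plain reading that the parenthesis limits both tests at week 4. If it were meant for viral load alone, the LFT conflict at week 4 would go, but the viral-load conflict and the missing week 16 would remain.

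The documents give no rate of ALT elevation, so no number of missed events is claimed. The SVR12 analysis is not affected by the LFT schedule.

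**What to change.** - Remove the Child's A restriction on the week-4 LFT in section 2.5 item 8a and in the matching Study Procedures item. LFTs are then drawn at weeks 4, 8 and 12 in all patients, and at week 16 on 16-week courses.
- State separately who has the week-4 viral load: all patients, as the table marks, or Child's A only.
- Add week 16 to the visit table, and say whether its week-1 LFT mark is intended. In the same edit, place the post-treatment viral load for 16-week courses at 16 + 12 = week 28.
- If dosing is already complete, state in the safety report which schedule was followed.

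Changing the table and the Risk section to match the text would also end the conflict, but it would leave patients without cirrhosis with no listed LFT from drug start to week 8.

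**Cost.** At most one extra LFT panel per patient without cirrhosis relative to the text: 25 x 1 = 25 to 30 x 1 = 30 in total. The documents give no cirrhosis share. Assuming 10% to 30%, the range is 25 x 0.7 = 17.5 (about 18) to 30 x 0.9 = 27. Relative to the table's week-4 mark, no panels are added. Blood is taken during dialysis. Patients on ribavirin, on warfarin, or positive for a hepatitis B marker already have a week-4 draw, so for them it is one more assay on the same draw.

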Please note: If the initial answer to this question is "no", but a gift is received during the conduct of this research study, the answer must be updated to "yes" upon receipt of the gift.

Regulatory Sponsor

Name
Type

IND Sponsor

Name
Department/School/Division
Phone
Fax
Pager
Email

Industry Sponsor

Sponsor Name
Contact Name
Street Address
Street Address (continued)
City, State/Province, Zip/Postal Code
Phone Number
Fax Number
Email Address
CRO Name
CRO Contact Person
CRO Street Address
CRO Street Address (continued)

CRO City, State/Province, Zip/Postal Code
CRO Phone
CRO Fax
CRO Email
Send bills for IRB to

Project Funding*

Is this project funded by or associated with a grant or contract?
Yes

Proposal Number	Title
10063958	"Real World" Administration of Zepatier (Grazoprevir plus Elbasvir) in Chronic Hemodialysis Patients

You are required to submit a copy of the grant, minus appendices, for review by the IRB.
Funding Application
There are no documents attached for this item.

Sponsor Funding

Is this study funded by an industry sponsor?
Yes

The University of Pennsylvania IRB charges fees to industry sponsors to cover the costs associated with the IRB's review and related administrative responsibilities. No fees are charged for studies funded by grants, non-profits, or internal funding.

For further information regarding the IRB Fee Policy, please visit:
http://www.upenn.edu/regulatoryaffairs/index.php?option=com_content&task=view&id=19&Itemid=8

Status of contract

Complete

[Back to submission activity](#) [Previous](#) [Next](#)

Send questions or comments about this site to: [contact] or [contact] -
Please do not include confidential information in your Email.

Copyright © 2007, [University of Pennsylvania](http://www.upenn.edu). All rights reserved.
[Statement on privacy](#)

Basic Info	Personnel	Site	Sponsors	IRBS	Protocol	Populations	Procedures	Consent	Risk/Benefit	Confirmation
------------	-----------	------	----------	------	----------	-------------	------------	---------	--------------	--------------

Protocol Form - Multi-Site Research

[Back to submission activity](#)
[Previous](#)
[Next](#)

Site Information

Management of Information for Multi-center Research where a Penn Investigator is the Lead Investigator of a multi-center study, or Penn is the lead site in a multi-site study. Provide a plan for the management of multi-site information that may be relevant to the protection of human research participants, such as:

- Reporting unanticipated problems involving risks to participants or others.
- Reporting of interim results.
- Coordination of protocol modifications.

PLEASE NOTE: This information must be included if Penn is the lead/data coordinating site.

There are no documents attached for this item.

Other Sites

Other Sites participating in the study

Management of Information for Multi-Center Research

- Reporting unanticipated problems involving risks to participants or others.
- Reporting of interim results.
- Coordination of protocol modifications.

[Back to submission activity](#)
[Previous](#)
[Next](#)

Send questions or comments about this site to: [contact] or [contact]. Please do not include confidential information in your Email.

Copyright © 2007, [University of Pennsylvania](#). All rights reserved.
[Statement on privacy](#)

Basic Info	Personnel	Bio	Sponsors	Sites	Populations	Procedures	Consent	Risk/Benefit	Confirmation
------------	-----------	-----	----------	-------	-------------	------------	---------	--------------	--------------

Protocol Form - Details of Protocol

[Back to submission activity](#)
[Previous](#)
[Next](#)

Abstract

We propose a "real world" observational study of Hepatitis C treatment in a cohort of prevalent dialysis patients. We will study response to therapy in the "real world" setting and identify barriers to treatment.

Objectives

Overall objectives

The primary objective is to develop real world strategies for the successful treatment of hepatitis C hemodialysis patients using Zepatier in a hemodialysis unit with a high prevalence of hepatitis C to improve patient outcomes and to reduce the risk of in-facility transmission of hepatitis C. These strategies developed will be primarily directed to Nephrologists and Hemodialysis Personnel (Nurses, Social Workers, Dieticians) in order that these individuals will gain the knowledge to administer a hepatitis C eradication program using Zepatier in their hemodialysis centers

Primary outcome variable(s)

The specific real world measures to be developed and summarized in this protocol are:

- Identify hepatitis C patients who meet the virologic and medical criteria for treatment with Zepatier alone or in combination with ribavirin
- Identify necessary pretreatment clinical and laboratory assessments that are needed before initiating treatment with Zepatier.
- Identify appropriate treatment candidates.
- Identify clinical and laboratory testing to monitor during treatment.
- Perform post-treatment testing of sustained virologic response to treatment (SVR at 12 weeks).

Secondary outcome variable(s)

Secondary outcomes include:

- Identifying steps required to obtain 3rd party insurance approval
- Identify barriers to third-party payment of treatment and steps necessary to overcome these barriers.
- Identify the roles of a clinical pharmacologist and non-physician health care personnel such as a dialysis nurse, social worker, and dietician in a Zepatier treatment protocol of hepatitis C infected dialysis patients.
- Identify available patient assistance programs for drug obtainment and criteria needed to qualify for such assistance.

Background

Hemodialysis patients have an exceptionally high prevalence of hepatitis C, with prevalence rates up to 25% in urban hemodialysis units in the United States and greater than 50% in less developed countries. It has been estimated that by 2020, 775,000 patients with ESRD will need dialysis in the United States and 109,000 of these patients will be infected with hepatitis C. Hepatitis C is associated with an increased mortality among hemodialysis patients with a relative risk of 1.59 (95% CI, 1.33- 1.86). Kidney transplant recipients with hepatitis C also have an increased mortality with a relative

risk of 1.79 (95% CI. 1.57-2.03). In addition hepatitis C infected transplant patients have an increased death rate from infection in the early (6 months) post-transplant period and a decreased graft survival. Attempts to prevent nosocomial transmission of hepatitis C in dialysis units by implementing universal precautions have not been consistently successful. The introduction of direct acting antivirals (DAAs) in 2011 as a treatment of hepatitis C patients has created a paradigm treatment shift for these patients. The DAAs have been shown to be highly effective with SVR rates greater than 90 to 95% in treatment naïve hepatitis C infected patients in the general population. One DAA, Zepatier is well suited for treatment of hemodialysis patients as well as patients with stage 4 or 5 chronic kidney disease not requiring hemodialysis since less than 1% of this DAA is excreted by the kidney. A recent randomized double-blind multicenter study compared Zepatier to placebo in stage 4 and 5 chronic kidney disease patients most of whom were hemodialysis dependent (77%) and who had infection with hepatitis C genotype 1. A SVR at 12 weeks after the end of therapy was achieved in 99% of patients who received Zepatier.

The majority of hemodialysis patient care is provided by nephrologists and hemodialysis healthcare personnel. Both of these caregiver groups have become quite adept at providing protocol driven medical care uniquely suited to this population and care setting. Although hemodialysis patients often have primary care providers and other medical specialists who participate in their care, dialysis patients are often reluctant to see these non-Nephrology physicians due to their demanding dialysis schedule. Furthermore, non-Nephrology providers often feel uncomfortable providing care and prescribing medications to patients with severely impaired renal function. Thus, nephrologists and hemodialysis personnel are uniquely situated to implement and monitor treatment protocols using DAAs such as Zepatier in dialysis unit patients with hepatitis C infection. Clear and current guidelines for the implementation and monitoring of DAA treatment protocols in the hemodialysis population currently do not exist, and the development of such guidelines is one of the purposes of this protocol. While nephrologists and hemodialysis health care personnel are aware of the prevalence of hepatitis C in hemodialysis patients and that DAAs are now available for treatment of such patients, most nephrologists and hemodialysis personnel are not aware of the specific real world steps required to identify and treat such patients

One aim of our study is to provide the specific real world steps which must be taken to successfully treat hepatitis C hemodialysis patients with DAAs. Application of these steps will allow hemodialysis units to implement guidelines which will allow DAA treatment of all eligible patients in a timely manner, thus reducing or eliminating the health consequences of hepatitis C infection in this special population. This real world protocol will be developed and implemented by a diverse group of investigators, each with a unique area of expertise needed for such a protocol development with real world implementation. Members of the investigative team include physicians with expertise in nephrology, hepatology, infectious disease, infection control, transplant nephrology and non-physician personnel with expertise in clinical pharmacology and hemodialysis social services.

Study Design

Phase*

Phase IV

Design

This is a prospective, non-randomized, non-blinded interventional trial of treatment of Hepatitis C with Zepatier.

Study duration

- Estimated length of time to enroll all subjects and complete the study
- Length of a subject's participation time in study
- Project date of the proposed study

We estimate this study will take no more than 1 year to complete. We have already identified all of the Hepatitis C antibody positive patients in the dialysis unit via routine clinical screening for Hepatitis C performed for standard of care dialysis center protocol. We anticipate study participants will require 9 months to complete the study. We anticipate it will take up to 3 months to obtain all of the necessary laboratory results and insurance approvals to obtain Zepatier. Patients will be treated for 12-16 weeks depending on resistance testing results. We will then follow the patients for 12 weeks after the completion of therapy to prove they have achieved a sustained viral response (SVR) or cure.

Resources necessary for human research protection

The investigator will retain copies of CRFs (or electronic files), and source documents for the maximum period required by the country in which the study will be conducted, or the period specified by the Sponsor, whichever is longer. If the investigator withdraws from the study (e.g., relocation, retirement), the records should be transferred to a mutually agreed upon designee (e.g., another investigator, IRB). Notice of such transfer will be provided in writing to the sponsor. Patients have access rights to their data and the possibility to rectify the data according to local law and procedures. They can discuss this issue further with the PI or by direct inquiries to the local data privacy officer representative of the sponsor. We have adequate number of coordinators with many years of experience in clinical trials. They have completed the CTTI Patient-Oriented Research Certification program, HIPPA training, and the Health and Radiation Safety (EHRS) training program as well as attending Human Subject Research workshops and the Clinical Research Coordinators (CRC) Forums. It is the site's responsibility to ensure the patients data remains confidential. There will be no secondary use of the data. The only way data will be used is the way described in protocol. In all the data recordings a code will replace the patients name. All the data collected will be kept confidential. The sponsors authorized personnel will enter the data in a computer database. Members of health authorities, the University of Pennsylvania Institutional Review Board or other persons required by law may review the data provided. This data may also be used in publications about the study drug. However, patients identity will not be revealed in any compilations, study reports or publications. Representatives from the sponsor, sponsor affiliates, health authorities and the IRB/IEC may access patients medical records. Such checks will only be done by qualified and authorized personnel. All such persons are required to and will keep the data confidential.

[Back to submission activity](#)
[Previous](#)
[Next](#)

Send questions or comments about this site to: [contact] or [contact] - Please do not include confidential information in your Email.

Copyright © 2007, [University of Pennsylvania](#). All rights reserved.
[Statement on privacy](#)

Basic Info	Personnel	Bio	Sponsors	Sites	Protocol	Randomize	Procedures	Consent	Risk/Benefit	Confirmation
------------	-----------	-----	----------	-------	----------	-----------	------------	---------	--------------	--------------

Protocol Form - Characteristics of the Study Population

[Back to submission activity](#)
[Previous](#)
[Next](#)

Target population

All prevalent adult hemodialysis patients with genotype 1 or 4 hepatitis C infection.

Subjects enrolled by Penn Researchers

30

Subjects enrolled by Collaborating Researchers

0

Accrual

The principal investigator rounds at the dialysis unit where the study will be conducted; thus he encounters potential study participants in the course of routine dialysis patient care.

The planned primary analysis will be the proportion of patients who following treatment have achieved a SVR at 12 weeks following completion of treatment.

Secondary analyses will determine (a) proportion of patients for whom third party approval for Zepatier treatment was successfully obtained (b) logistic barriers to getting third party approval (c) adverse events with treatment

Key inclusion criteria

All potential study participants must be hepatitis C viral load positive in order to enroll. Those who are antibody positive but viral load negative have either spontaneously cleared their infection or else been previously treated with other therapies. Additionally subjects must:

- Age: Be 18 or greater on day of signing informed consent
- HCV treatment status must fall into one of following categories (1) Naïve to all anti HCV treatment (2) Prior INF or PEG IFN plus ribavirin treatment failures (null responders, partial responders, relapses) (3) Intolerant to prior INF or PEG-INF plus ribavirin regimen (4) Prior HCV NS3/4A protease inhibitor failures.
- Not of reproductive potential hemodialysis patient with 12 months of no menses. Women of childbearing potential should use 2 reliable forms of contraception simultaneously during treatment and for 6 months after completion of therapy. This guideline will be applied for both Zepatier treatment alone or when combined with Ribavirin.
- Maies with partners of reproductive potential as long as contraception is used during and for 6 months after completion of therapy. This guideline will be applied for both Zepatier treatment alone or when combined with Ribavirin.
- Understand the study procedures, alternative treatments available, risks involved with the study, and voluntarily agrees to participate by giving informed written consent.
